To achieve the primary aim, MR elastography will be performed in up to 104 healthy children, somewhat evenly divided (approximately 48 each) into two age groups (7-<12years, 12-<18years). Means, standard deviations and 95% confidence intervals for normal liver stiffness will be calculated for each age group and values will be compared across groups.

Multi-site secondary aims and hypotheses are as follows:

- To assess cross-platform variability in normal MRI liver stiffness values. We hypothesize that there will be no significant difference in mean normal liver stiffness values obtained on three different vendor platforms (GE, Philips, Siemens).
- 2. To assess for cross-field strength variability in normal MRI liver stiffness values. We hypothesize that there will be no significant difference in mean normal liver stiffness values obtained at 1.5T versus 3T.
- 3. To assess for sex-related (male vs. female) differences in normal MRI liver stiffness values. We hypothesize that there will be no sex-related differences in normal liver stiffness measured by MR elastography.

To achieve secondary aim #1, subject recruitment will be stratified across sites with approximately 32 subjects in each age group being imaged on each of the different vendor platforms (GE, Philips, Siemens). To achieve secondary aim #2, subject recruitment will be stratified across 1.5T and 3T magnets with approximately 48 subjects in each age group being imaged at each of the different field strengths. To achieve secondary aim #3, approximately equal numbers of male and female subjects will be recruited in each of the two age groups.

CCHMC exploratory aims and hypotheses are as follows:

1. To determine normal corrected T1 (cT1) values for two pediatric age groups. We hypothesize that there will be no significant difference in mean cT1 values between age groups or between field strengths.

Overall research strategy:

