We propose to conduct a multi-institutional study of normal liver stiffness values in pediatric subjects with no known history of liver disease. The requirement for multiple sites relates to the need to acquire normative stiffness values on each of the three major MRI vendor platforms to assess for unexpected cross-platform variability in liver stiffness. CCHMC has Philips MRI scanners (1.5 and 3T) equipped with MR elastography but does not have access to GE or Siemens MRI scanners in a research environment. Massachusetts General Hospital (MGH) has an elastography capable GE scanner (1.5T), Children's Hospital of Philadelphia (CHOP) has elastography-capable GE and Siemens scanners (3T), and Mallinckrodt Institute of Radiology (MIR) has an

elastography-capable Siemens scanner (1.5T). This human study protocol will be submitted for approval to the Institutional Review Board at CCHMC. CCHMC will serve as the lead site. CHOP, MGH and MIR may choose to submit to their IRB or to rely on the CCHMC IRB.

Power calculation relevant to SA1: Determine normal liver stiffness values (and associated normal ranges) as measured by MR elastography for three pediatric age groups: Based on the standard deviation of normal liver stiffness measurements in the study by Etchell et al. (SD=0.3 kPa) and the confidence intervals from a study of healthy adult livers by Lee et al. (95% CI ~±0.1 kPa), we calculate that a sample size of n=18 is needed in each group to achieve 2-sided 95% confidence intervals with a distance from the mean to the limits that is equal to 0.15 kPa for each group [Etchell, Lee]. This sample size also provides 80% power to detect an effect size (Cohen's d) of 0.67 between the two age groups. Given the prior study findings of a correlation between subject age and liver stiffness, we will recruit into two subject age groups (7-<12years, 12-<18 years). Based on prior published and unpublished MRI studies of "healthy volunteers" at CCHMC, we expect up to 25% of "healthy subjects" recruited for this study will have unsuspected liver disease manifest as abnormalities in liver function tests or liver fat fraction values greater than 5% by MRI proton density fat fraction (PDFF) (12). Therefore, we will increase recruitment targets by 25% over the levels required to achieve adequate statistical power. Thus, approximately 24 subjects will be recruited to each group at each field strength for a total study recruitment of n= up to 104.

MR imaging:

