Healthy pediatric subjects without a known history of liver disease will be recruited via advertising through established hospital channels (e.g. email) and posted flyers and/or posters at each of the study sites. Based on prior studies of normal subjects at CCHMC, we anticipate no difficulty recruiting the required number of subjects for this study. For a prior study of pancreatic function in normal subjects that required MRI and placement of an intravenous catheter, 142 responses expressing interest in participating in the study were received within 4 days of study announcement.

For each age group, MRI vendor and field strength, approximately half the recruited subjects will be male and half will be female. CCHMC will recruit a total of 32 subjects (16 male, 16 female), CHOP will recruit up to 40 subjects (approximately 20 male, 20 female), and MIR and MGH will each recruit a total of 16 subjects (8 male, 8 female).

Inclusion criteria:

- 1. Age 7-less than 18 years of age
- No documented history of liver disease
- 3. English speaking*

Exclusion criteria:

1. NPO less than 4 hours

- 2. Body mass index < 10th or > 85th percentile for age
- 3. Documented history of liver disease
- 4. Pregnancy
- 5. Inability to lie still for duration of the MRI
- 6. Inability to breath hold for the duration of the 15-20 second MR elastography sequence
- 7. Standard contraindication to MRI (implanted hardware, etc.)
- 8. Requirement of sedation or general anesthesia for MRI
- 9. Abnormality of any prior measured liver function test**
- 10. Any prior liver fat fraction > 5% by MRI PDFF**

*English speaking has been included as an inclusion criterion as successful performance of an MRE examination requires following detailed and repeated breath hold instructions. This is a multicenter study and interpreter services are not uniformly available in the imaging research environment across participating institutions.

**Research results meeting this exclusion will eliminate subjects from population analysis

7. PROCESS OF OBTAINING CONSENT:

Participants will be screened in advance of enrollment by study personnel to determine baseline eligibility for participation. Once eligibility has been confirmed, written informed consent will be obtained in person at the time of the research visit.

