Written informed consent will be obtained in person from parents/guardians of subjects <18 years of age. In addition to parent/guardian informed consent, assent will be obtained from all subjects ≥11. Consent or assent may be obtained by study personnel inclusive of the PI, Co-Is or clinical research coordinator(s).

8. STUDY PROCEDURES:

To confirm "healthy status" and the absence of liver disease, subjects will be weighed and measured (height and waist circumference) prior to the research MRI.

Subjects will be surveyed about liver health using a survey created with the assistance of the study hepatologist and medical records (if available) will be reviewed to exclude documented liver disease (ATTACHMENT A).

Subjects will also undergo a research venous blood draw to confirm absence of elevation of markers of liver health inclusive of: AST, ALT, GGT, alkaline phosphatase, total and direct bilirubin. This research blood draw will require 2.5 mL of venous blood and will occur prior to or following the research MRI. At CCHMC the research blood draw will occur in the Schubert Research Center by SRC nursing staff. In addition, the research MRI will include a PDFF sequence to measure liver fat fraction in all subjects to identify previously unknown fatty liver disease.

Study visit structure (single visit):

1. Intake survey and anthropomorphic measurements

- 2. MRI safety screening
- 3. Research MRI exam
- Research blood draw

Drugs, Devices, and Biologics:

MR elastography equipment consists of an active and a passive driver system. The passive driver is connected to the active driver in the equipment room by a wave-guide with a hollow plastic tube. The active driver generates low amplitude (60 Hz) vibrations which are passed via pneumatic pressure to the passive driver. The initiation and cessation of the vibrations are controlled by the MR pulse sequence programmed and embedded as part of the scanner software. All MRE pulse sequences and hardware to be used for this study are sold as product by the MR vendors or an aftermarket company (Resoundant, Inc.) and all are FDA approved.

The other MRI sequences to be utilized in this study (anatomic, PDFF) are FDA approved sequences sold as product by the MRI hardware vendors.

9. DATA ANALYSIS/METHODS:

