All PDFF and MR elastography images will be processed both locally and centrally at a single site (CCHMC) by a single trained observer to ensure uniformity in post-processing technique. Post-processing will be performed as previously described with placement of single large regions of interest in the right hepatic lobe (12). Central MR elastography data will be post-processed using MRE Lab (Mayo Clinic, Rochester, MN) and PDFF data will be post-processed using Philips Intellispace (Philips Healthcare, Best, The Netherlands).

De-identified cT1 data acquired at CCHMC only will be sent to Perspectum Diagnostics for analysis.

Descriptive statistics will be utilized to describe the characteristics of each subject group (age, sex, scanner manufacturer, field strength). Normal liver stiffness for each age group will be summarized as mean ± std with range and 95% confidence interval also provided. Two sample t-test or one-way analysis of variance (ANOVA) will be used to assess for differences in liver stiffness between age groups and between different groups of categorical variables (sex, scanner manufacturer, field strength). The correlation between liver stiffness and continuous variables will be assessed by using Pearson on Spearman correlation coefficients as appropriate. Multiple linear regression models will be utilized to evaluate the association between liver stiffness and the predictor variables adjusting for all other covariates. Box plots will be generated to visually illustrate the results from the group comparisons mentioned above. All analyses will be performed using SAS version 9.4. A p-value less than 0.05 will be considered statistically significant for all inference testing.

10. FACILITIES and PERFORMANCE SITES:

Research blood draws will occur in the Schubert Research Clinic. All other study procedures will occur in the CCHMC Imaging Research Center (IRC).

11. POTENTIAL BENEFITS:

There are no direct benefits to study participants. This research, however, is critical for our understanding of normal MRE values in children which are relevant to the diagnosis of disease utilizing MRE. Therefore this research has potential future benefit to children with known or suspected liver disease.

12. POTENTIAL RISKS, DISCOMFORTS, INCONVENIENCES AND PRECAUTIONS:

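### The stratum sizes for secondary aims 1 and 2 each imply 192 children against 96 to 104 planned, and the 80% power at d = 0.67 is attached to 18 per group when it needs 36 per age group

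*Combined protocol and SAP*

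**What the plan says.** Section 4 (Study Design) plans up to 104 children, about 48 in each of two age groups. It then sets two recruitment strata:

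- Secondary aim 1 (vendor): "approximately 32 subjects in each age group being imaged on each of the different vendor platforms (GE, Philips, Siemens".
- Secondary aim 2 (field strength): "approximately 48 subjects in each age group being imaged at each of the different field strengths".

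The power paragraph in the same section instead has "approximately 24 subjects will be recruited to each group at each field strength for a total study recruitment of n= up to 104". It justifies n = 18 in each group by a 95% confidence-interval half-width of 0.15 kPa with SD 0.3 kPa. The next sentence says that this sample size also gives 80% power for Cohen's d of 0.67 between the two age groups.

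On capacity, Section 4 states that "CCHMC has Philips MRI scanners (1.5 and 3T) equipped with MR elastography" and lists Philips at no other site. It lists GE at 1.5T for MGH, Siemens at 1.5T for MIR, and GE and Siemens at 3T for CHOP. Section 6 sets the quotas: "CCHMC will recruit a total of 32 subjects (16 male, 16 female), CHOP will recruit up to 40 subjects", and "MIR and MGH will each recruit a total of 16 subjects (8 male, 8 female". Section 8 describes one attendance per child ("Study visit structure (single visit") with one research MRI. Section 9 plans t-tests or ANOVA between age groups and "between different groups of categorical variables (sex, scanner manufacturer, field strength".

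**The concern.** Section 4 gives four sites recruitment targets that conflict with the plan's own total, with the cell size in its power paragraph and with the quotas in Section 6. Secondary aims 1 and 2 hypothesise no difference, so a null result can be read only against the number of children behind it. Taken literally, the text gives those comparisons about twice the children who will be enrolled.

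The power sentence concerns the primary hypothesis, the difference between age groups. The only sample size stated before it is 18 in each group. A reader who takes it at its word would think 18 evaluable children per age group sufficient, for instance if exclusions for abnormal liver tests or fat fraction ran high.

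**Working it through.** **Stratum totals (inputs from Sections 4 and 6)**

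- Vendor strata as written: 32 × 2 age groups × 3 vendors = 192.
- Field-strength strata as written: 48 × 2 age groups × 2 strengths = 192.
- Power paragraph: 24 × 2 × 2 = 96.
- Site quotas: 32 + 40 + 16 + 16 = 104.
- Ratio: 192/104 = 1.85; 192/96 = 2.0.

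**Can any stratum be filled?** The documents do not say how CCHMC divides its scans between 1.5T and 3T, or how CHOP divides its scans between GE and Siemens. The maximum below therefore credits each stratum with every child the relevant sites could supply.

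| Stratum | Needed as written | Maximum available |
|---|---|---|
| Philips | 32 × 2 = 64 | CCHMC 32 |
| GE | 64 | MGH 16 + CHOP 40 = 56 |
| Siemens | 64 | MIR 16 + CHOP 40 = 56 |
| 1.5T | 48 × 2 = 96 | MGH 16 + MIR 16 + CCHMC 32 = 64 |
| 3T | 96 | CHOP 40 + CCHMC 32 = 72 |

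Every stratum falls short. These maxima would hold even if every CCHMC child were scanned on both magnets and every CHOP child on both vendors, so repeat scanning does not rescue the text. By contrast, 96/3 = 32 and 96/2 = 48, so the two figures match totals over both age groups.

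**Precision, the plan's own figure.** Half-width = t(0.975, n−1) × SD/√n. With SD 0.3 this is 0.154 kPa at n = 17 and 0.149 kPa at n = 18. The n = 18 reproduces.

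**Power, the plan's own figure.** Two-sample t-test, α = 0.05, d = 0.67. The noncentrality is d√(n/2), with n per age group.

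| n per age group | d√(n/2) | Two-sided t-test | Two-sided normal approximation |
|---|---|---|---|
| 18 | 0.67 × √9 = 2.01 | 49.7% | 52.0% |
| 36 | 0.67 × √18 = 2.84 | 80.1% | 81.1% |

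The stated 80% does not reproduce at 18. A one-sided t-test there gives 62.7%. The required n for 80% is 35.96, so 36. With 18 per age group, 80% power needs d = 0.96.

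**Link to recruitment.** 18/0.75 = 24 per age-by-field-strength cell. Two cells make 48 recruited per age group, and 48 × 0.75 = 36 evaluable. At the ceiling of 104, 104 × 0.75 = 78, or 39 per age group, with power 83.2%.

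**What the doubling means for aims 1 and 2.** The plan states no detectable difference for these aims. For illustration, these are the differences detectable with 80% power at two-sided 0.05, unadjusted, with SD 0.3 kPa and age groups pooled (d × 0.3):

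| Comparison | Implied n per group | Planned n per group |
|---|---|---|
| Vendor pair, enrolled | 64: 0.499 × 0.3 = 0.15 kPa | 32: 0.711 × 0.3 = 0.21 kPa |
| Vendor pair, after 25% loss | 48: 0.578 × 0.3 = 0.17 kPa | 24: 0.826 × 0.3 = 0.25 kPa |
| Field strength, enrolled | 96: 0.406 × 0.3 = 0.12 kPa | 48: 0.578 × 0.3 = 0.17 kPa |
| Field strength, after 25% loss | 72: 0.470 × 0.3 = 0.14 kPa | 36: 0.670 × 0.3 = 0.20 kPa |

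**The case against.** The strongest reply is that this is an editorial slip. The figures that drive enrolment agree: up to 104 in total, about 48 per age group, 24 per group and field strength, and quotas summing to 104. No site would recruit towards 192. In the power paragraph, if a group means an age-by-field-strength cell, then 18/0.75 = 24 fits, each age group has 36 evaluable children, and the 80% is right. The plan claims no power for aims 1 and 2, so no stated claim about them becomes false.

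Much of this is fair. The enrolment plan is coherent, the authors very probably calculated with 36, and the detectable differences above illustrate scale only. But the stratum sizes are still wrong by a factor of about two, which the word approximately cannot absorb. The number 36 is never written, and as worded the power sentence points to 18. The cell reading supports the correction and does not remove the need for it.

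Two smaller objections concern the remedy. Totals of 32 per vendor add to 96, not 104: with all 104 enrolled and 32 on Philips, GE and Siemens share 72, an average of 36 each. That is within an approximate target. And Section 9 does not say outright that age groups are pooled for the vendor and field-strength tests. Pooling is the natural reading and should be stated.

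**Conclusion.** Both errors stand and should be corrected. The strata for secondary aims 1 and 2 imply 192 children against 96 to 104 planned, 1.85 to 2.0 times too many, and no vendor or field-strength stratum can be filled under any division of scans at CCHMC and CHOP. The power statement for the primary age comparison gives the wrong n as written: about 50% at 18 per age group, 80% at 36.

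This does not show an underpowered design; the planned enrolment supports the age comparison even at the worst-case 25% loss. The power figures assume a two-sided test, since Section 9 gives the 0.05 level without sidedness, but 18 per group fails one-sided as well. The stratum finding needs only the documents' own counts and scanner list.

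**What to change.** In Section 4:

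- **Aim 1:** restate as about 32 children in total on each vendor platform, about 16 per age group.
- **Aim 2:** restate as about 48 children in total at each field strength, about 24 per age group.
- **Both aims:** say that the comparisons in Section 9 pool the two age groups. Exact counts depend on how CCHMC and CHOP divide their scans, so state that division if it is known.
- **Power paragraph:** keep n = 18 for the confidence-interval width, and attach 80% power at d = 0.67 to 36 evaluable children per age group (18 at each of two field strengths).
- **If detectable differences are added for aims 1 and 2:** give them for the pooled comparisons, separately at enrolled and at evaluable numbers.

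The cost is protocol wording only, with no added children and no change to the planned analyses. The stated stratum sizes become half as large.

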There is one prior study of healthy pediatric patients that included 35 subjects (24 between ages 5-14 years and 11 between ages 15-18 years)[Etchell]. That study demonstrated that normal liver stiffness values were lower for healthy pediatric subjects than for healthy adult subjects (2.2 vs. 2.6 kPa). The authors also found a slight significant correlation between age and liver stiffness (r=0.38) but failed to demonstrate a difference in liver stiffness between subjects ≤14 years of age versus >14 years of age. While this prior study provides some information about normal liver stiffness in the pediatric population, it has key limitations. First, this study was performed with nonstandard multi-frequency MR elastography. One of the frequencies that was utilized (56 Hz) is close to the standard 60 Hz MR elastography utilized for clinical MRE, but differences in frequency utilized to measure tissue stiffness are known to influence liver stiffness measurements and thus normative data from this study may not apply to MR elastography performed with manufacturer standard technique. Second, the subjects imaged in this study were not fasting at the time of MR imaging. There are conflicting data regarding the effect of fasting (or lack thereof) on measured liver stiffness with some studies showing a stiffening effect of increased post-prandial splanchnic blood flow [Hines, Lemoine, Yin]. Third, while the subjects included in this study had no "known history of liver disease" MR fat fractions were not measured and serum liver function tests were not checked to confirm liver health. Finally, all examinations in this prior study were performed on a single manufacturer MR platform and at a single field strength, possibly limiting generalizability across other platforms.

MR elastography is a rapidly evolving technique and sequence improvements are constantly being developed. Additionally, new MRI techniques for assessment of diffuse liver disease are constantly being developed. At CCHMC only, additional imaging data will be acquired for exploratory aims related to these newer techniques.

4. STUDY DESIGN:

Study aims and hypotheses are as follows:

Primary aim/hypothesis – To determine normal liver stiffness values (and associated normal ranges) as measured by MR elastography for two pediatric age groups. We hypothesize that normal liver stiffness as measured by MR elastography will differ between the two pediatric age groups, increasing with increasing age.

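### A non-significant cT1 comparison with about 12 to 16 children per side cannot by itself show that cT1 is the same across age groups or field strengths

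*Combined protocol and SAP*

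**What the plan says.** The cT1 work is exploratory and confined to one site. Section 3 of the protocol says: "At CCHMC only, additional imaging data will be acquired for exploratory aims related to these newer techniques". Section 4, under the CCHMC exploratory aims, has two sentences on cT1. The first is an estimation aim: normal cT1 values for each of the two age groups. The second is comparative: "We hypothesize that there will be no significant difference in mean cT1 values between age groups or between field strengths".

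Section 6 fixes the number available: "CCHMC will recruit a total of 32 subjects (16 male, 16 female"). Section 4 says "CCHMC has Philips MRI scanners (1.5 and 3T) equipped with MR elastography", so both field strengths are available there. It also anticipates that up to a quarter of recruits will turn out to have unsuspected liver disease. Section 6 removes such children from the population analysis.

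On analysis, Section 9 says of cT1 only this: "De-identified cT1 data acquired at CCHMC only will be sent to Perspectum Diagnostics for analysis". The summaries, t-test or ANOVA, and regression in that section are written for liver stiffness. The inference criterion is general: "A p-value less than 0.05 will be considered statistically significant for all inference testing". No cT1 standard deviation, sample size, power statement or equivalence margin is given.

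**The concern.** The hypothesis is phrased as the absence of statistical significance. Judged as it is worded, a test with p of 0.05 or more would satisfy it, and small groups make that outcome likely whether or not cT1 differs. The plan offers nothing else, such as a margin or a CI criterion, by which the hypothesis could be judged.

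At stake is how the normal cT1 values are presented. The aim names values by age group but not by field strength. A non-significant field-strength comparison could therefore be taken as grounds for quoting values that apply equally at 1.5T and 3T, when the data may be compatible with a sizeable difference.

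**Working it through.** **The plan's own sample-size figures (liver stiffness, Section 4).** The CI half-width is t(0.975, n−1) × SD/√n. With SD 0.3 kPa and n = 18 this is 0.149 kPa, against the target of 0.15 (n = 17 gives 0.154). Inflating for 25% loss, 18/(1 − 0.25) = 24. Both figures reproduce. The stated 80% power at d = 0.67 reproduces with 36 per age group, that is 18 at each of two field strengths (80.1%). With 18 per group, power is 49.7%. None of these figures was set for cT1.

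**Inputs for cT1.**
- Recruits: 32 (Section 6), at CCHMC only (Section 9).
- Two age groups and two field strengths (Section 4). An even split, 32/2 = 16 per side, is assumed. It fits the site totals: 16 at CCHMC plus 16 at each of the two sites listed with a single 1.5T scanner gives 48 at 1.5T.
- Exclusions: 0 to 25%, so 16 × 0.75 = 12 at the lower end.
- Alpha 0.05, taken as two-sided. A two-sample t-test is assumed, because no cT1 test is named.
- Differences in SD units (d), because no cT1 SD is given. The values 0.5, 0.8 and 1.0 are generic benchmarks. The value 0.67 is the plan's own benchmark for stiffness.

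**Power.** This comes from the noncentral t with 2n − 2 degrees of freedom and noncentrality d√(n/2). For d = 0.5 the noncentrality is 0.5 × √6 = 1.22 at n = 12 and 0.5 × √8 = 1.41 at n = 16.

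| True difference (SD) | Power, 12 per side | Non-significant | Power, 16 per side | Non-significant |
|---|---|---|---|---|
| 0.5 | 21.6% | 78.4% | 27.8% | 72.2% |
| 0.67 | 34.8% | 65.2% | 45.0% | 55.0% |
| 0.8 | 46.6% | 53.4% | 59.1% | 40.9% |
| 1.0 | 64.9% | 35.1% | 78.1% | 21.9% |

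The difference detectable with 80% power is 1.20 SD at 12 per side and 1.02 SD at 16.

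**Precision.** The 95% CI half-width for a difference is t(0.975, 2n − 2) × √(2/n) in SD units:
- n = 12: 2.074 × 0.408 = 0.85 SD
- n = 16: 2.042 × 0.354 = 0.72 SD

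**What a claim of sameness would need.** Two one-sided tests at 0.05, with a true difference of zero and 80% power, need roughly n = 2[(1.645 + 1.282)/m]² per side, where m is the margin in SD units. For m = 0.5 this is 2 × 5.854² = 68.5, so 69. The table gives simulation-checked results over an assumed range of margins.

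| Margin (SD) | Needed per side | Power at 12 | Power at 16 |
|---|---|---|---|
| 0.5 | 69 | 0.2% | 0.8% |
| 0.67 | 39 | 6% | 18% |
| 0.8 | 28 | 22% | 43% |
| 1.0 | 18 | 54% | 74% |
| 1.25 | 12 | 82% | 93% |

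**The case against.** The strongest reply is that the plan never says a non-significant test will be taken as proof of sameness. Section 9 defines when a difference is declared and does not say what follows otherwise. It names no cT1 test at all. That is correct. A reader might infer that the plan commits to confirming the hypothesis by p of 0.05 or more, but the documents do not state such a rule. What stands is narrower: the hypothesis is worded in terms of significance, and no other criterion is supplied.

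A reader might also infer that the study means to publish one cT1 value for all ages. The documents do not support this, since the first sentence of the aim asks for values in two age groups. The worry about pooling applies mainly to field strength.

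A third tempting reading is that these numbers could never support a conclusion of similarity. That goes too far. With 12 to 16 per side, an equivalence test would have 82 to 93% power for a margin of 1.25 SD. If cT1 varies little among healthy children, even ±0.85 SD might be narrow in absolute terms. The documents give neither the SD nor a margin, so this cannot be settled.

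It is also fair to say that the aim is exploratory, and that similar wording in the multi-site secondary aims bears more directly on the study's main product. Both limit the weight of the point. Neither makes a non-significant p-value evidence of no difference.

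**Conclusion.** The point holds in limited form. With about 12 to 16 children per side, a non-significant cT1 comparison by age group or field strength is weak evidence of similarity. A true difference of 0.5 SD would be missed 72 to 78% of the time. At the plan's own stiffness benchmark of 0.67 SD, non-significance would still be the likelier result, at 55 to 65%. The plan neither guards against reading this as sameness nor sets out a cT1 analysis that would show how wide the uncertainty is.

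This rests on an even split at CCHMC, exclusions between none and the plan's upper bound of 25%, a two-sided t-test, and generic effect sizes. The conclusion is the same at both ends of the range. Twelve per side is the lower end, not the expected number. The point does not affect the estimation of cT1 values by age group as an aim, nor the primary and secondary stiffness aims. It is minor: worth correcting, but not essential to the study.

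**What to change.** Keep the first sentence of the cT1 aim. Replace the second with estimation of the age-group difference and the field-strength difference.

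Add cT1 to Section 9:
- mean, SD and 95% CI for each age group and each field strength;
- both differences with 95% CIs from one linear model containing age group and field strength;
- a statement that a non-significant p-value will not be reported as no difference.

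An equivalence margin is needed only if the investigators wish to claim sameness. In that case it should be fixed in advance in milliseconds, with the 90% CI for the difference required to lie inside it.

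The cost is a few lines of protocol text and one model, with no additional children, scans or visits. The price is a more cautious cT1 conclusion.
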